**Table 2 - Data Documentation Schedule**

Assessment/ Procedure (only available data to be collected; no diagnostic or monitoring procedures to be applied to the patients apart from those of routine clinical practice)	Baseline	Treatment Period			Post-treatment (PT) Period		
		On-treatment visits	Mid treatment visit for pts receiving 24 weeks of therapy	EoT b	Early PT visit	SVR 12 visit	SVR 24 visit
Patient authorization	X a						
Demographic information	X						
IL28B	X						
Relevant CHC disease characteristics	X						
Liver fibrosis stage	X					X	X
CHC treatment history	X						
HCV genotype and subtype	X						
HCV RNA samples	X	X	X	X	X	X	X
Clinical chemistry and hematology	X	X	X	X	X	X	X
ABBVIE REGIMEN initiation documentation	X						
ABBVIE REGIMEN adherence		X	X	X			
Concomitant medication	X	X	X	X			
Relevant medical history, co-morbidities	X						
sAE, AE and pregnancy reporting	X	X	X	X	X c	X d	X d
For patients receiving RBV: Evidence, in accordance with local label, that female patient or female partner of male patient is not pregnant	X						
Patient questionnaires – FACIT-F	X	X	X	X		X	X
Patient questionnaires – WPAI	X			X		X	X
Patient questionnaires – PRISM	X					X	X
Patient questionnaires – PAM-13	X			X			

Abbreviations: EoT = End of Treatment (at Week 12 or 24 or at premature discontinuation),  
PT = Post-Treatment

- a Written patient authorization must be obtained before any data documentation in the eCRF
- b Patients who prematurely discontinue should return to the site to document EoT data
- c Tolerability documentation until PT week 4
- d Pregnancy reporting for patients treated with DAA plus RBV

In accordance with the non-interventional nature of the study all HCV RNA measurements will be performed at the sole discretion of the physician and all HCV RNA measurements have to be entered into the eCRF. All recorded HCV RNA values will be assigned to appropriate time points (baseline, on-treatment visits, EoT visit, post-treatment visits) as follows:

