**Table 3 - Analysis Time Windows for HCV RNA**

Phase	Time point	Time Window
Pre-Treatment	Baseline	Last value prior to start of study treatment (i.e. $\leq$ study day 1)
On-treatment		Study day during treatment period^# (Study day 1 = first treatment day)
Treatment Week	4 (RVR*)	15 - 42^
EoT	Actual EoT	Study day of last dose# (28 days prior to last dose - 7 days post last dose)
Post Treatment	12 weeks (SVR 12 window)	$\geq$ 70-126 days post last dose
	24 weeks (SVR24 window)	127-210 days post last dose
	48 weeks (SVR48 window)	> 210 days post last dose

^values must also be  $\leq$  7 days post last dose

#  $\geq$ study day 2

\*RVR = rapid virological response

All reported safety laboratory test results will be assigned to one of the time points using the time windows specified in the table below.

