#### 4.2.3 Handling of missing data

No data will be imputed for any effectiveness or safety analyses except for the analyses of the HCV RNA endpoints and certain PRO endpoints. The discussion of missing data imputation for the PRO endpoints is included in section 4.2.7.2.3.

HCV RNA values will be selected for an RVR, EOTR and SVR analysis based on visit windows as defined in Table 4. When there is no HCV RNA value in a visit window based on defined visit windows, the closest values before and after the window, regardless of the value chosen for the subsequent and preceding window, will be used for the flanking imputation described below. For analysis of RVR, EOT and SVR, if a subject has a missing HCV RNA value at a post-Day 1 visit but with undetectable or unquantifiable (LLoD or LLoQ  $\leq$ 50 IU/mL) HCV RNA levels at both the preceding value and succeeding value, the HCV RNA level will be considered undetectable or unquantifiable, respectively, at this visit for this subject. In addition, if a subject has an

unquantifiable HCV RNA level at the preceding value and an undetectable HCV RNA level at the succeeding value, or vice versa, the HCV RNA level will be imputed as unquantifiable at this visit for this subject.

For analyses of RVR, subjects still missing a value for the visit after flanking imputation will be considered as a failure. For EoTR and SVR analysis, if there is no value in the appropriate window after flanking imputation but there is an HCV RNA value after the window, then it will be imputed into the EoTR or SVR window respectively. Subsequent to this flanking and backward imputation, if the HCV RNA value remains missing at a specific time point, then the subject will be considered as virological failure at this time point (i.e., not undetectable or unquantifiable).

If a subject starts another treatment for HCV, then all HCV RNA values for this subject measured on or after the start date of the new HCV treatment will be excluded from analyses. The subject will be considered a failure for summaries of viral response at all time points after the start of the new HCV treatment.

Due to the non-interventional nature of this study several different methods for determination of the HCV RNA value can be applied. For the purpose of the statistical analysis, a HCV RNA measurement is considered <50 IU/mL,

- if a PCR test was used

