##### 4.2.7.2 Secondary Variables

###### 4.2.7.2.1 Secondary Effectiveness Variables

###### Response

For the other response rates (i.e. RVR, SVR24 , SVR48, EoT response rate, relapse rate, viral breakthrough), the simple percentage of patients and a two-sided 95% confidence interval (CI) of the percentage will be computed (based on the Wilson's score method) as well. The RVR and EoT response rates will be reported for CP and the SVR24 and SVR48 rates will be reported for the respective CPSFU, stratified by genotype and cirrhosis status and overall. The relapse rates will be estimated stratified by SVR window (i.e. during SVR12 window=relapse12, during SVR24

window=relapse24, after SVR24 window=relapselate) and stratified by genotype and cirrhosis status and overall in patients of the CP with EoT response who fulfilled the following criteria:

- completed treatment as defined previously,
- had at least one HCV RNA measurement  $\geq 70$  days post-treatment or was a treatment failure between EoT and 70 days post-treatment.

Viral breakthrough rates [defined as at least one documented HCV RNA  $<50$  IU/mL followed by HCV RNA  $\geq 50$  IU/mL during treatment] will be estimated overall and stratified by genotype and cirrhosis status in all patients of the CP, who have at least one undetectable or unquantifiable, on-treatment HCV RNA measurement and at least one on-treatment or EoT measurement thereafter.

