#### 4.2.9.2 Second Interim Analysis

A second IA was performed in October 2016 (data snapshot: 5 October 2016).

The first IA was updated. Furthermore, the following analyses were performed:

Site information and researcher experience were displayed, as well as patient disposition by genotype and cirrhosis status for the EP.

The CP and SP were restricted to patients with planned treatment duration of 12 weeks who started DAA treatment before 1st April 2016.

The following tables were created for the restricted CP

- treatment regimen
- socio-demographic characteristics
- CHC disease characteristics
- CHC Related laboratory variables at baseline
- other key laboratory variables at baseline
- CHC treatment history in treatment experienced patients
- Co-morbidities and co-infections
- alcohol consumption
- CD4 and HIV-RNA in patients with HIV at baseline
- PRISM, FACIT Fatigue Subscale Score (not normed), WPAI, PAM13 over time
- Premature Termination of Treatment and its Main Reason
- Virological Response Rates (Virological response rates will be displayed in the CPSFU12 and in patients with an evaluable HCV RNA test result as well.)

All tables were structured by genotype and cirrhosis status, except for the analyses regarding questionnaires. These analyses were structured by treatment regimen and cirrhosis status.

Additionally, the impact of various explanatory covariates (patient and disease characteristics) at baseline on SVR12 was analyzed. Opiate substitution was added as additional covariate and age will be categorized ( $\geq 70$ / $< 70$  years) here. (No interaction was taken into account.)

For the restricted SP the following tables will be created:

- Treatment-emergent AEs
- Serious Treatment-emergent AEs

The tables will be structured by treatment regimen and cirrhosis status.

The analyses were repeated replacing cirrhosis status once by age ( $\geq 70$ / $< 70$  years) and once by opiate substitution (no/ yes; yes, is defined as patients with psychoactive substance dependency - opiate substitution)

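### RVR counts CP patients with no week-4 HCV RNA test as failures, so the rate is biased downward, and the SAP text plans no count of untested patients and no rate among those tested

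*SAP*

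**What the plan says.** **Missing week-4 values.** SAP 4.2.3 first tries flanking imputation, using "the closest values before and after the window, regardless of the value chosen for the subsequent and preceding window". A missing value becomes negative (undetectable or unquantifiable, with an assay limit of at most 50 IU/mL) only if there are negative "HCV RNA levels at both the preceding value and succeeding value". If that fails, then for RVR "subjects still missing a value for the visit after flanking imputation will be considered as a failure".

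**Contrast with later time points.** Backward imputation from a later value comes in the next sentence, but not for RVR: "For EoTR and SVR analysis, if there is no value in the appropriate window after flanking imputation", a later value may be carried back.

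**Windows.** SAP Table 3 sets week 4 at study days 15-42, and the value must be no later than 7 days after the last dose. Baseline is the "Last value prior to start of study treatment", day 1 included. (SAP 4.2.3 points to Table 4 for these windows; the HCV RNA windows are in Table 3.)

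**Testing.** Under SAP Table 2, "all HCV RNA measurements will be performed at the sole discretion of the physician".

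**Population.** SAP 4.2.7.2.1 states: "The RVR and EoT response rates will be reported for CP". Response rates are also tabulated for patients who completed treatment and for the non-core population (SAP Table 8).

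**Evaluable-only display.** For the second interim analysis (SAP 4.2.9.2), response rates were to be shown "in patients with an evaluable HCV RNA test result as well". The final-analysis text contains no such display.

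**The concern.** A patient who is not tested on days 15-42 but is negative at week 8, at end of treatment and at SVR12 will usually be reported as a week-4 failure. Such a patient cannot be told apart from one who was tested and still viraemic.

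The other response rates have some protection that RVR lacks. SVR12 is repeated in the core population with sufficient follow-up (CPSFU), and its non-response table has a separate category for missing data. SVR24 and SVR48 are reported in their CPSFU sets. CPSFU is defined by post-treatment follow-up, so it does nothing for a missing week-4 test. The completer table applies the same missing-value rule.

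At stake is how a secondary endpoint is read. A low RVR could mean slow early response, sparse testing or both, and the outputs described in the SAP text do not separate them.

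**Working it through.** **1. The plan's own figure.** The only precision figures are for SVR12 (SAP Table 1). The Wilson limits are [p + z²/2n ± z·√(p(1−p)/n + z²/4n²)] / (1 + z²/n). With p = 0.95 and z = 1.96:

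- n = 620: 92.99 to 96.46, width 3.47 (plan: 93.0 to 96.5, 3.5)
- n = 590: 92.93 to 96.49, width 3.55 (plan: 92.9 to 96.5, 3.6)
- n = 62: 86.49 to 98.26, width 11.77 (plan: 86.5 to 98.3, 11.8)

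Table 1 reproduces. Neither document gives a planning figure for RVR.

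**2. When flanking can work.** The preceding value must come from before day 15. Patients have confirmed chronic hepatitis C, so baseline is expected to be viraemic, and the only route is a negative test on days 2-14. For a 12-week regimen the SAP plans five visits and two interim windows. Protocol Annexes 5 and 6 name the interim contacts as one early on treatment and one early after treatment, which leaves one planned on-treatment contact before end of treatment. Its timing is in Figure 1, which was not available in the text I worked from. Rescue is therefore possible but should be uncommon.

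**3. Size of the bias.** Let m be the share with no value on days 15-42, r the true response (assumed the same in tested and untested patients), and s the share of missing cases that flanking rescues:

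reported RVR = (1 − m)·r + m·s

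All three are assumptions. With s = 0:

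| m | r = 80% | r = 90% | r = 95% |
|---|---|---|---|
| 10% | 72.0% | 81.0% | 85.5% |
| 20% | 64.0% | 72.0% | 76.0% |
| 30% | 56.0% | 63.0% | 66.5% |
| 40% | 48.0% | 54.0% | 57.0% |

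At r = 90% and m = 20%, rescue of 10% or 25% of missing cases raises the 72.0% to 74.0% or 77.0%.

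**4. The interval.** At n = 620 and an assumed r = 95%, the Wilson interval is 93.0 to 96.5 with nobody untested, 82.5 to 88.1 at m = 10%, 72.5 to 79.2 at m = 20% and 62.7 to 70.1 at m = 30%. The last three exclude the assumed true rate, because the interval reflects sampling error only.

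**5. Do untested patients make up most of the failures?** The non-RVR share is (1 − m)(1 − r) + m(1 − s), of which m(1 − s) is untested. This reaches one half when m = (1 − r) / [(1 − s) + (1 − r)]. With s = 0, the break-even m is 4.8% at r = 95%, 9.1% at r = 90%, 16.7% at r = 80% and 23.1% at r = 70%.

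**6. What the count of untested patients would add.** If r is the rate among those tested, the CP rate must lie between (1 − m)·r and (1 − m)·r + m. For r = 90% and m = 20%, that is 72% to 92%. A reader needs m to form this range.

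**The case against.** **Counting missing as failure is prespecified and conservative.** Protocol 9.7.1 already treats a value still missing at a time point as virological failure, and Protocol 9.9 warns that missing HCV RNA data can lead to underestimation (said of SVR). This stands, and it is why the rate should be kept.

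**Withholding backward imputation from RVR is sound.** A negative week-8 value does not show that week 4 was negative. This also stands; the lack of backward imputation is not a defect.

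**Evaluable-only RVR has a bias of its own.** It assumes that testing is unrelated to response. It also omits very early stoppers: a week-4 value must be within 7 days of the last dose, so a patient whose last dose falls before study day 8 (15 − 7) can have none. This stands, so that rate belongs beside the other and should not replace it.

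**Table layouts are in Part II of the SAP, which is not among the documents.** If the shells already show these numbers, the remaining change is to say so in 4.2.7.2.1.

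**Stronger readings that the documents do not support.** A reader might infer that flanking can never rescue a patient; a negative test on days 2-14 followed by a negative value after day 42 does. A reader might infer that RVR mainly measures how often sites test; that needs a testing rate and an expected RVR, neither of which is given, and the 28-day window limits missingness. A reader might infer that differences between strata reflect testing habits; the strata are genotype and cirrhosis status, and nothing shows that testing differs between them. Nor is RVR confined to the full CP, given the completer and non-core tables, although these do not remove untested patients.

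**Conclusion.** The point holds as a reporting weakness in a secondary endpoint. The planned RVR rate combines response with testing frequency and is biased downward by untested patients whom flanking does not rescue. None of the other populations or tables described in the final-analysis text corrects or reveals this.

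The size is unknown. The fall from 90% to between 81% and 54% rests on an assumed true RVR of 90%, an assumed 10-40% untested, no rescue, and equal response in tested and untested patients. If nearly everyone is tested on days 15-42, the bias is small.

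The consequence is limited. RVR was added in SAP 4.1.2 and is not among the endpoints in Protocol 9.7.3.2. It is not a listed covariate in the SVR12 regression models, and the primary SVR12 analysis does not depend on it.

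**What to change.** In SAP 4.2.7.2.1, keep the RVR rate for the CP with missing counted as failure, and describe it as a conservative estimate. Beside it, for the same genotype and cirrhosis strata, report:

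- the number of CP patients with no HCV RNA value on days 15-42 after flanking;
- the RVR rate, with Wilson interval, among patients with an evaluable value in that window.

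The second interim analysis already showed response rates in patients with an evaluable result, and all the data are collected. Because RVR is not a protocol-listed endpoint, the addition changes none.

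The cost is one extra rate row and one count per stratum. The rate has a different denominator, which must be labelled. A footnote should say that it assumes testing is unrelated to response and leaves out patients who stop very early.

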**Table 2 - Data Documentation Schedule**

Assessment/ Procedure (only available data to be collected; no diagnostic or monitoring procedures to be applied to the patients apart from those of routine clinical practice)	Baseline	Treatment Period			Post-treatment (PT) Period			
		On-treatment visits	Mid treatment visit for pts receiving 24 weeks of therapy	EoT b	Early PT visit	SVR 12 visit	SVR 24 visit	SVR 48 visit
Patient authorization	X a							
Demographic information	X							
IL28B	X							
Relevant CHC disease characteristics	X							
Liver fibrosis stage	X					X		X
CHC treatment history	X							
HCV genotype and subtype	X							
HCV RNA samples	X	X	X	X	X	X	X	X
Clinical chemistry and hematology	X	X	X	X	X	X	X	X
ABBVIE REGIMEN initiation documentation	X							
ABBVIE REGIMEN adherence		X	X	X				
Concomitant medication	X	X	X	X				
Relevant medical history, co-morbidities	X							
sAE, AE and pregnancy reporting	X	X	X	X	X c	X d	X d	X d
For patients receiving RBV: Evidence, in accordance with local label, that female patient or female partner of male patient is not pregnant	X							
Patient questionnaires: FACIT-F	X	X	X	X		X		X
Patient questionnaire: WPAI	X			X		X	X	
Patient questionnaire: PRISM	X					X		X
Patient questionnaires: PAM-13	X			X				
Patient questionnaire: PSP e (U f )			X		X			
Patient questionnaire: PSP e (U f & S g )		X		X		X		

Abbreviations: EoT = End of Treatment (at Week 12 or 24 or at premature discontinuation),  
PT = Post-Treatment

- a Written patient authorization must be obtained before any data documentation in the eCRF
- b Patients who prematurely discontinue should return to the site to document EoT data
- c Tolerability documentation until PT week 4
- d Pregnancy reporting for patients treated with DAA plus RBV
- e applicable for patients enrolled in the PSP
- f Utilization
- g Satisfaction

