#### 9.4.1.5 Concomitant Medication

Concomitant medication - the following will be documented:

- Concomitant medication used from the time when the decision is made to initiate treatment with the ABBVIE REGIMEN until after the last dose

It should be verified by the treating physician that concomitant medication can be safely administered with the ABBVIE REGIMEN (including ritonavir) and RBV. Some medications may be contra-indicated, some may require dose adjustments due to potential for drug-drug interactions (DDIs). The investigator or qualified designee should review the concomitant medication(s) labels and screen concomitant medications at each visit for potential DDIs.

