#### Confidential Information

No use or disclose outside AbbVie is permitted without prior written authorization from AbbVie  
 Version 3.0. (22. Apr 2015) – Germany V3.0 (17. November 2016)

Page 34 of 63

Access to the EDC system will be provided for the duration of the study through a password-protected method of internet access. To obtain a user account for the eCRF application of a project, the user has to contact the data management Support Team. Each user receives his/her individual user account with user name and password to his/her personal email address only. After the registration, the user receives an email with the personal details. The email contains the user name, password and the link to the application. Each user has an own access to the productive eCRF (group accounts are not accepted). For identity protection, it is not allowed that users pass on their access codes to other persons. All actions of a user are assigned to a user within the database. Confirmed actions are considered to be the electronic equivalent of a user's signature, and are therefore saved in the data base.

Examinations, diagnostic measures, laboratory assessments, findings and observations routinely performed in patients with CHC included in this cohort, will be transcribed by the investigator or designee from the source documents into the eCRF. Only data specified in the protocol will be entered into the eCRF. For each enrolled patient, the investigator or designee will create a new patient file in the eCRF and a unique patient number will be automatically allocated by the system.

If a patient withdraws Informed Consent, data documentation is immediately stopped. Study data obtained up to the date Informed Consent has been withdrawn can be used for analyses if not explicitly revoked by patient. If use of the data has been explicitly revoked by patient, data will be deleted from the eCRF (but still remains in the audit trail for regulatory purposes).

A comprehensive data validation program utilizing front-end checks in the eCRF will validate the data. Automated checks for data consistency will be implemented; discrepancies need to be solved by the researcher in the eCRF before the module can be completed.

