## 9.7 Data Analysis

### 9.7.1 Analysis Population, Time Windows and Handling of Missing Data

The target population (TP) is defined as all patients who fulfill the criteria specified in Section 9.2.1. The core population (CP) is defined as all patients of the TP, who have started the treatment combination recommended in the current local label for their disease characteristics. Patients not receiving the treatment recommended in the local label will be summarized in the non-core population (NCP). In addition, the core population with sufficient follow-up data (CPSFU) is defined as all CP patients, who fulfil one of the following criteria:

- (1) evaluable HCV RNA data  $\geq 70$  days after the last actual dose of the ABBVIE REGIMEN (i.e. data within the SVR12 time window)
- (2) a HCV RNA value  $\geq 50$  IU/mL at the last measurement post-baseline (i.e. no virological response achieved at the last measurement on-treatment or post-treatment)
- (3) HCV RNA  $< 50$  IU/mL at the last measurement post-baseline, but no HCV RNA measurement  $\geq 70$  days after the last actual dose of the ABBVIE REGIMEN due to reasons related to safety (e.g. dropped out due to AE) or incomplete efficacy information (e.g. virologic failure such as relapse is reported in the eCRF but date and value of the corresponding HCV RNA test is missing). This means only patients who had virological response at their last on-treatment or post-treatment measurement, but had no HCV RNA measurements  $\geq 70$  days post-treatment for reasons not related to safety or effectiveness (e.g. lost-to-follow-up or patient not willing to perform an additional HCV RNA test  $\geq 70$  days post-treatment) will be excluded from this analysis.

The Safety Population (SP) is defined as all patients who received at least one dose of the ABBVIE REGIMEN.

In accordance with the non-interventional nature of the study all HCV RNA measurements will be performed at the sole discretion of the physician and all HCV RNA measurements have to be entered into the eCRF. All recorded HCV RNA values will be assigned to appropriate time points (baseline, on-treatment visits, EoT visit, post-treatment visits). The time windows for the assignments will be specified in the statistical analysis plan (SAP).

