No data will be imputed for any effectiveness or safety analyses except for the analyses of the HCV RNA endpoints. When there is no HCV RNA value in a visit time window post-baseline, but prior to EoT, the closest values before and after the window, regardless of the value chosen for the subsequent and preceding window, will be used for the flanking imputation described below. If a patient has a missing HCV RNA value at a post-baseline visit prior to EoT but has undetectable HCV RNA (with LLoD  $\leq 50$  IU/mL) or unquantifiable, but detectable HCV RNA levels (with LLoQ  $\leq 50$  IU/mL) at both the preceding and succeeding measurements, the HCV RNA level will be considered undetectable or unquantifiable, respectively, at this visit for this patient. In addition, if a patient has an unquantifiable HCV RNA level at the preceding measurement and an undetectable HCV RNA level at the succeeding measurement, or vice versa, the HCV RNA level will be imputed as unquantifiable at this visit for this patient. For virological response at EoT a corresponding backward imputation approach will be applied. This means if HCV RNA is missing at EoT, then unquantifiable or undetectable will be assumed for EoT, if the succeeding HCV RNA value is undetectable or unquantifiable. For SVR12 the single last available HCV RNA measurement  $\geq 70$  days post-treatment will be used. Subsequent to this flanking and backward imputation, if the HCV RNA value remains missing at a specific time point, then the patients will be considered as virological failure at this time point (i.e. not undetectable or unquantifiable).

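### The SAP's re-treatment rule needs a start date that neither document schedules for collection, and its backward imputation has no guard, so a re-treated relapser can count as an SVR responder

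*SAP*

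**What the plan says.** **The rule.** SAP 4.2.3 opens its rule with "If a subject starts another treatment for HCV, then all HCV RNA values for this subject measured on or after the start date" and excludes those values once the other therapy has begun. It continues: "The subject will be considered a failure for summaries of viral response at all time points after the start of the new HCV treatment".

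**Medication data.** Protocol 9.4.1.5 defines what is documented as "Concomitant medication used from the time when the decision is made to initiate treatment with the ABBVIE REGIMEN until after the last dose". In protocol Table 2 and the SAP's copy of it, the concomitant medication row is marked at baseline, on treatment, mid-treatment and EoT, and at no post-treatment visit. The post-treatment list in protocol 9.4.1.3 covers laboratory data including HCV RNA, tolerability and pregnancies, and questionnaires. Protocol 9.6.1 adds: "Only data specified in the protocol will be entered into the eCRF".

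**HCV RNA data.** Protocol 9.7.1 requires that "all HCV RNA measurements have to be entered into the eCRF", and observation runs to 48 weeks after treatment (protocol 9.2.2). The SAP windows are days 70-126 for SVR12, days 127-210 for SVR24 and after day 210 for SVR48 (SAP Table 3).

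**Imputation.** Flanking imputation in SAP 4.2.3 needs an undetectable or unquantifiable value on both sides of the gap. Backward imputation does not: "if there is no value in the appropriate window after flanking imputation but there is an HCV RNA value after the window", that later value is placed in the EoT or SVR window. No condition is set on the value before the window.

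**The concern.** The re-treatment rule works only if the start date of the new therapy is known. As specified, medication documentation ends with the studied regimen, while HCV RNA is entered for almost another year. Patients in whom the regimen failed are the natural candidates for another one. If the switch is not recorded, their later negative values are analysed as if the studied regimen had produced them. A negative value while still taking the new drug is enough.

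Backward imputation opens a second gap. Even when the relapse itself is in the database, a later negative value can fill an empty SVR window. The plan's own rule then produces a responder who also fits one of its non-response categories. The primary endpoint is exposed along with SVR24 and SVR48, and every such error is in the favourable direction.

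**Working it through.** **1. Trace the rules for one patient.** Treatment completed; HCV RNA <50 IU/mL at EoT; ≥50 on post-treatment day 28; switch to another regimen with no recorded date; no test on days 70-126; <50 on day 200.

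- Exclusion rule: cannot act, because there is no start date.
- Flanking for SVR12: fails, because the preceding value (day 28) is viraemic.
- Backward imputation: the day-200 value goes into the SVR12 window, so the patient is an SVR12 responder.
- SVR24: day 200 lies in days 127-210, so the patient is also an SVR24 responder.
- Relapse: the patient meets the definition in SAP 4.1.2 and the relapse non-response category in SAP 4.2.7.2.1. The SAP does not say which classification prevails.

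**2. Other routes when the switch is unrecorded.**

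- *SVR12 with a filled window:* the clock starts at the last dose of the studied regimen. A patient who stops or relapses early and switches promptly can be <50 on days 70-126 because of the new drug.
- *SVR24 and SVR48:* a patient viraemic in the SVR12 window stays an SVR12 failure. A value <50 after re-treatment, on days 127-210 or after day 210, makes the same patient an SVR24 or SVR48 responder. That patient also enters the corresponding CPSFU through having evaluable data.

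**3. Reproduce the planned precision.** Inputs from protocol 9.5 and SAP 3.2: SVR12 95%, n = 620, 590 and 62, two-sided 95% Wilson interval. The limits are [p + z²/2n ± z√(p(1−p)/n + z²/4n²)] / (1 + z²/n).

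- n=620: 92.99 to 96.46, width 3.47 (plan: 93.0 to 96.5, 3.5)
- n=590: 92.93 to 96.49, width 3.55 (plan: 92.9 to 96.5, 3.6)
- n=62: 86.49 to 98.26, width 11.77 (plan: 86.5 to 98.3, 11.8)

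The plan's table is reproduced. The half-width at n=620 is 3.47/2, about 1.7 points.

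**4. Effect per misclassified patient.** Expected non-responders: 620 × 0.05 = 31. One misclassified patient adds 1/620 = 0.16 points, or 1/62 = 1.6 points in a subgroup of 62. Five move 589/620 = 95.00% to 594/620 = 95.81% (interval 93.93 to 97.12). About 10 to 11, a third of the 31, would equal the half-width.

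**5. Range for the empty-window route.** The documents give no count, so these are assumptions: all 31 failures are virological, 10-30% have no value on days 70-126, and 10-50% of those have a later negative value carried back.

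- Low: 31 × 0.10 × 0.10 = 0.31 patients; 0.31/620 = 0.05 points
- High: 31 × 0.30 × 0.50 = 4.65 patients; 4.65/620 = 0.75 points

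No figure is offered for the filled-window, SVR24 or SVR48 routes, because the documents give nothing to anchor one.

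**The case against.** **The eCRF may already hold the date.** The protocol lists are not a complete field list. The SAP uses items they do not name, such as units of alcohol and reasons for not completing the study, and one co-medication profile in SAP 4.2.8.2 concerns drugs reintroduced after treatment. The re-treatment rule itself presupposes a date. This stands as a limit: a reader might infer that re-treatment is not captured at all, but the documents show only that no field is specified. No SAP profile covers a drug first started after treatment.

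**There are partial safeguards.** Relapse can be recorded as a reason for not completing the study, and such a patient may have no later value to carry back. A relapser who completed treatment appears in the relapse table, so the conflict could be noticed. This stands, but no text lets either item override a later negative value. The relapse table also requires completed treatment, so it misses early stoppers.

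**The protocol's last-value rule.** Protocol 9.7.1 says "For SVR12 the single last available HCV RNA measurement" at or after day 70 is used, with no upper limit. A reader might infer that any late success of another regimen counts as SVR12. The SAP, which governs the analysis, ends the window at day 126, declares that change, and adds the re-treatment rule. Only the routes traced above remain.

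**Size.** A reader might apply a 10-50% conversion to all 31 failures and obtain 3 to 16 patients, or +0.5 to +2.6 points on SVR12. That ignores the empty-window condition on this route, and the non-response categories also include deaths, discontinuations and missing data. Nor can 16 conversions be set against an assumed SVR48 denominator of 300: at 95% that group would contain only 15 failures.

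**The study is descriptive.** There is no hypothesis test or decision threshold, and SVR24 and SVR48 are secondary. This lowers the priority but does not remove the misclassification.

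**Conclusion.** The point holds as a mismatch between an SAP rule and the data specified to support it, together with an imputation rule that lacks a guard. Applied as written, SAP 4.2.3 can turn a documented relapser into an SVR12 responder, in conflict with the SAP's own non-response categories. The SVR24 and SVR48 routes are broader.

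The bias can only raise SVR. Its size cannot be determined from the documents. The empty-window range of about +0.05 to +0.75 points on SVR12 rests on the assumed fractions in the working and lies below the planned half-width of about 1.7 points. A larger effect on SVR12 is not supported by the documents. It should be fixed before the final analysis, but it is not a reason to reject the primary analysis. If the eCRF holds the date, the data-capture part is settled by citing the field, and the imputation part remains.

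**What to change.** 1. **Data source.** Name in the SAP the existing eCRF field for new HCV treatment and its start date. If there is none, obtain both by retrospective query for every patient with HCV RNA ≥50 IU/mL at the last on-treatment or EoT measurement or at any post-treatment measurement, and for every early discontinuer. The trigger must be this wide because a patient who is viraemic on treatment or at EoT and switches directly may never have a post-treatment viraemic value. A new visit item alone would come late: inclusion was planned for about 12 months from November 2015, and the SAP already reports an August 2017 interim analysis.

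2. **Guard in SAP 4.2.3.** State that backward imputation into an SVR window is not applied when the last observed value before the window is ≥50 IU/mL, whether on treatment, at EoT or post-treatment. The patient is then a failure at that time point.

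3. **Sensitivity analysis.** Count any patient with a post-treatment value ≥50 IU/mL as a failure at that and all later SVR time points unless re-treatment is documented as absent. This should not be the primary rule: it turns an unanswered query into a failure, and protocol 9.9 already warns that missing HCV RNA data can lead to underestimated SVR.

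**Cost.** One targeted query, a sentence in SAP 4.2.3 and one additional analysis. About 31 non-responders are expected at 95%; the documents do not give the number of early discontinuers. Sample size and interval width do not change. The downside is that a rare false-positive value with no retest inside the window stays a failure.
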